3.5 Premature Discontinuation

Treatment may be discontinued prematurely for the following reasons:

- 1. Participant requests termination of the study medication;
- 2. Participant is intolerant of the study medication despite predetermined dose reductions and side effect management strategies;
- 3. Safety concerns at the discretion of the investigator. These concerns will be documented in the source documents.

Participants who discontinue treatment prematurely for the above reasons will be encouraged to remain in the post-treatment follow-up period for an additional 24 weeks, unless they withdraw consent. For those discontinued prematurely, blood samples will be obtained as listed for the week 48 end-of-treatment visit.

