2.2 Efficacy Endpoints

The primary endpoint in this study will be a sustained virological response 24 weeks post treatment. The durability of this response will be reassessed 48 weeks after stopping therapy. Secondary endpoints will be changes in HCV RNA levels at 24, 48, and 72 hours, 4 weeks, 24 weeks, and at the end of treatment. Other secondary endpoints will be sustained biochemical responses and improvements of serum alanine aminotransferase levels at 4 weeks, 24 weeks, and at the end of treatment. The definitions of responses are given below.

Sustained virological response: Measured at post treatment week 24, is defined as lack of detectable HCV RNA in serum, by qualitative PCR with a lower limit of sensitivity of 50 IU/ml (e.g., Roche, Amplicor HCV assay).

Durable sustained virological response: Measured 48 weeks following discontinuation of therapy is defined as absence of detectable HCV RNA in serum by qualitative PCR.

Changes in HCV RNA: Measured at 24 hours, 4 weeks, 24 weeks, and at the end of treatment will be assessed by quantitative PCR (Roche, Monitor HCV assay). Changes will be categorized as decreases of <1 log_{10} , 1-2 logs, >2 logs in IU, and negative (<50 IU) by qualitative PCR.

The primary endpoint of the study will be sustained virological response.

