Viral Genetics	Days 1, 2, 7, 14, 28, and weeks 8, 12, and 24. For responders, at end of treatment (48 weeks)
Viral Kinetics	Days 1, 2, 7, 14, 28, and weeks 8, 12, 24, and 36. For responders, at end of treatment (48 weeks)
Pharmacokinetics (PEG-IFN alfa-2a levels 2',5'- OAS serum activity)	Days 1, 2, 7, 14, 28, and weeks 8, 12, and 24. For responders, at end of treatment (48 weeks)
Serum Storage	Each visit (except weeks 6, 16, 20, 28, 32, 40, 44)
Interferon Signaling	Days 1, 2, 7, 14, 28

Table 7Safety and Efficacy Visits

Immunology (CD4/CD8)	Weeks 8, 24, and end of treatment (week 48 for responders), or at early termination visit
CES_D*	Weeks 4, 12, 24, 48
Symptom Assessment	Each visit (except days 1 and 2)
Questionnaire*	
Brief MATI	Weeks 4, 12, 20, 28, 36
Gratitude Letter	Weeks 12, 36
Telephone Call	Week 24-26 (pending viral studies)
MEMS Use Questionnaire*	Weeks 4, 8, 12, 16, 20, 24, 28, 32, 36, 40, 44, 48
Adherence Questionnaire*	Weeks 4, 12, 24, 36, 48
Social Support and Self-	Week 24
efficacy Questionnaire*	
Sexual Function	Weeks 4, 12, 24, 48
Questionnaire*	
Adherence Videos	Weeks 1, 4, 12, 24, 36
Data Collection from Electronic	Weeks 4, 8, 12, 16, 20, 24, 28, 32, 36, 40, 44, 48
Monitors	

*Also assessed at the time of early termination for patients who discontinue prior to Week 24.

4.5 Follow-up Period: Participants will be followed for an additional 48 weeks following end of treatment. Participants who responded to therapy at week 24 will be treated for 48 weeks. They will return for post-treatment follow-up visits at follow-up weeks 4, 12, 24, 36, and 48. Non-responders will be followed for 24 weeks only. During these visits, participants will be evaluated for resolution of adverse events and laboratory studies will be drawn to measure efficacy. Participants will be contacted by telephone on one occasion between follow-up visits in order to foster continuity and encourage adherence with study follow-up.

Follow-up visit Procedures						
Interim Medical History						
Symptom-directed Physical	Vital signs and weight at each visit; physical exam at weeks 12, 24,					
Exam	and 48, and as needed					
Adverse Event Assessment						
Concurrent Medication						
Assessment						
CBC/Differential	Each visit					
Chemistry	Each visit: ALT, AST, AlkPO4, direct bilirubin					
	Follow-up weeks 12, 24, 48: albumin, uric acid, BUN, creatinine,					
	glucose					
	Follow-up week 24: fasting triglycerides, glucose, insulin					

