6.0 Data Analysis/Statistical Power

The study is designed to have 400 patients; 200 White/Caucasian, 200 Black/African American. There will be 80% power to detect a difference in the percentages of undetectable viral RNA 6 months following treatment (sustained virological response, SVR) between racial groups if the percentage of White/Caucasian patients with a SVR is 40% and the percentage in Black/African-American patients is 26% using a two-sided test with α = 0.05. In multivariable analyses, there will be 80% power to detect a difference if the percentages of SVR are 40% for Whites/Caucasians and 25% for Blacks/African Americans, assuming a multiple correlation coefficient of 0.4 between race and the other independent variables using a two-sided test with α = 0.05.

Primary analyses will be performed using all enrolled patients. Patients will be considered enrolled in the study upon taking the first dose of study medication. Participants who do not have outcome data will be included as treatment failures. We will also perform analyses that include only those participants with known outcome data.

Summary statistics will be generated to describe the study sample at baseline. Descriptive statistics, including measures of central tendency (e.g. means, medians) and estimates of spread (e.g., standard deviations) will be used for continuous variables such as age. Frequency distributions will be used for categorical variables such as education level. Ninety-five percent confidence intervals will be calculated for all point estimates of continuous data. Graphical displays (e.g. histograms, box plots) will also be used to describe the data. The baseline demographic information and viral characteristics of the racial groups will be compared using the chi-square test for association or exact tests for differences in proportions or trend in ordinal data. Continuous variables may be transformed, where appropriate, to meet the assumptions of parametric tests. The Student's t-test or a non-parametric alternative, the Wilcoxon rank-sum test, will be used to determine differences in the distribution of continuous data between the two racial groups.

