The proportion of African Americans and Caucasians with SVR will be compared using the chi-square test of association. The association between race and SVR after adjusting for potential confounders such as adherence, HCV sub-genotype, initial viral level, ALT, body mass index, and baseline histology will be assessed through multiple logistic regression analyses. The Hosmer-Lemeshow statistic will be calculated to determine if there is evidence that the final multiple logistic regression model does not fit. ²³ These

analyses will be repeated for durable viral response, i.e., having undetectable viral RNA 12 months following treatment discontinuation.

Generalized estimating equation (GEE) methods of Zeger and Liang.^{24,25} will be used to assess the differences between the racial groups with respect to changes in serum HCV RNA levels during therapy. This approach models both the regression of the response variable on the independent variables and accounts for the correlated nature of the responses. Analyses using conventional regression methods could provide erroneous variance estimates and loss of statistical efficiency because of the conventional assumption that each response is statistically independent. As a result, invalid inferences could be made if the conventional approach were applied to these longitudinal data.

The models examining response to treatment will include measures of adherence. As an initial step in examining adherence, graphical displays of the dosing history of each participant will be plotted and compared to the prescribed dosing regimen. Graphs include chronological plots showing the date and time of dose intake and frequency histograms of inter-dose intervals. The inter-dose interval representing the length of time between two successive doses will be calculated. For ribavirin, the optimal inter-dose interval is 12 hours and for peginterferon it is 7 days. Longer dosing intervals represent non-adherence and times in which the participant theoretically did not have adequate inhibitory drug concentration. In addition, summary statistics of adherence such as the percentage of prescribed doses taken and the percentage of drug holidays will be derived from the MEMS cap data. GEEs with multiple responses and adherence as a time-dependent covariate will be examined.

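### Follow-up of participants who stop treatment early is stated as 24 weeks in one section and 48 in others; under the 24-week text, a sustained responder who stopped early has no sample for durable response

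*Protocol*

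**What the plan says.** Five parts of the protocol bear on this.

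- **Early stoppers.** For those who stop at their own request, for intolerance or for safety, Section 3.5 says: "Participants who discontinue treatment prematurely for the above reasons will be encouraged to remain in the post-treatment follow-up period for an additional 24 weeks". The sentence does not depend on HCV RNA status.
- **General follow-up.** Section 4.5 opens with "Participants will be followed for an additional 48 weeks following end of treatment" and then limits only non-responders to 24 weeks. The Summary also gives 48 weeks after therapy ends. Section 3.1 gives responders 48 weeks and non-responders 24, counted from completing therapy, with response judged by PCR at treatment week 24.
- **Endpoints.** Section 2.2: "The primary endpoint in this study will be a sustained virological response 24 weeks post treatment". Durable SVR is "Measured 48 weeks following discontinuation of therapy is defined as absence of detectable HCV RNA in serum by qualitative PCR".
- **Analysis set and missing data.** Section 6.0: "Patients will be considered enrolled in the study upon taking the first dose of study medication" and "Participants who do not have outcome data will be included as treatment failures". The next sentence adds: "We will also perform analyses that include only those participants with known outcome data".
- **Durable response.** After describing the chi-square and logistic analyses of SVR, Section 6.0 says that these "analyses will be repeated for durable viral response, i.e., having undetectable viral RNA 12 months following treatment discontinuation".

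**The concern.** The clock for durable SVR starts when therapy stops, so a participant who stops early can in principle achieve it. The 24-week limit costs nothing for week-24 non-responders, who are HCV RNA positive in duplicate. Section 3.5 applies the same limit to people who may be undetectable at post-treatment week 24.

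Under that text, such a person is a success on the primary endpoint, has no visit at which durable SVR could be observed, and becomes a failure through the missing-data rule. Tolerability of treatment is then mixed into a measure meant to describe durability. The Summary names durable SVR beside SVR as a comparison between the racial groups, so this matters beyond description. Because the sections disagree, sites could also follow different texts, and missing week-48 data would then depend on site.

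**Working it through.** The protocol states no figure for durable SVR, so there is none to reproduce. The check is to set the passages side by side and then size the effect under stated assumptions.

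**Step 1: does any section schedule a week-48 visit for an early stopper with SVR?**

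| Source | Who is covered | Follow-up after therapy |
|---|---|---|
| Summary | participants generally | 48 weeks |
| Section 3.1 | responders / non-responders at treatment week 24, from completing therapy | 48 / 24 weeks |
| Section 3.5 | those stopping for request, intolerance or safety | 24 weeks, encouraged |
| Section 4.5, opening | participants generally | 48 weeks |
| Section 4.5, visit list (weeks 4, 12, 24, 36, 48) | week-24 responders treated for 48 weeks | 48 weeks |
| Section 4.5, limit | non-responders | 24 weeks |

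Only Section 3.5 is specific to early stoppers, and it stops at 24 weeks. The general statements would give them 48. No section expressly schedules weeks 36 and 48 for them. Anyone who stops before treatment week 24 never reaches the PCR that defines responder status, so Section 3.1 does not classify that person.

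**Step 2: how many could be misclassified if Section 3.5 is followed?**

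Inputs from Section 6.0: 200 per group; design SVR of 40% (Caucasian) and 26% (African American), that is 200 × 0.40 = 80 and 200 × 0.26 = 52 expected responders.

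Assumptions, not in the protocol: a share e of 10-20% stops early; a share s of 10-20% of those reaches SVR; all of these responses are durable.

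Sustained responders without a week-48 sample, per group = 200 × e × s:

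- low: 200 × 0.10 × 0.10 = 2 (1 percentage point)
- high: 200 × 0.20 × 0.20 = 8 (4 percentage points)

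As a share of expected responders this is 2/80 = 2.5% to 8/80 = 10% in Caucasians, and 2/52 = 3.8% to 8/52 = 15.4% in African Americans.

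**Step 3: what happens to the race difference?**

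For illustration, take the design SVR rates as the true durable rates. The observed rate is then the design rate minus e × s.

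- Equal e and s in both groups: both rates fall by the same amount and the difference stays at 40 − 26 = 14 points.
- e = 10% in Caucasians, 20% in African Americans, s = 20% in both: (40 − 2) − (26 − 4) = 38 − 22 = 16 points.
- The reverse: (40 − 4) − (26 − 2) = 36 − 24 = 12 points.
- Equal e of 20%, with s of 20% in one group and 10% in the other: also 12 or 16 points, depending on which group has the higher s.

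**The case against.** The strongest reply is that the 48-week statements already cover these people. Someone undetectable at treatment week 24 who stops at week 30, for example, is a responder under Section 3.1 and can be read as having 48 weeks of follow-up. Section 3.5 nowhere says that later visits are withheld. This part stands: a reader might infer that early stoppers become durable failures by settled design, and the document does not support that. It supports a contradiction, with this result if Section 3.5 governs.

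Second, the missing-equals-failure rule stands in a paragraph on the primary analyses, and the primary endpoint is SVR at 24 weeks. Its reach to durable SVR comes from the later sentence repeating the analyses. That is the natural reading, but it is an inference.

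Third, a known-outcome analysis is planned and would not score these participants as failures. That is true, and it tempers the point. It does not remedy it: the analysis leaves out people selected by tolerability, and their week-48 result stays unknown.

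Fourth, a larger effect is tempting. With 20% stopping and 30% SVR among them, 12 of the 52 expected African American responders (23%) would be affected. But then 12 of 40 early stoppers respond (30%), against (52 − 12)/160 = 25% of everyone else. Section 5.0 points the other way: it reports higher SVR among those who received at least 80% of dose and duration (48% against 41%, and 63% against 54%, each compared with the full intention-to-treat result). That upper figure should not be used.

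**Conclusion.** The concern holds as a contradiction between Section 3.5 and the 48-week follow-up text, with a definite consequence if Section 3.5 is followed: early stoppers with SVR have no week-48 sample and are counted as failures in the main durable-SVR analysis.

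The size is modest. About 2-8 of 200 per group are affected, resting wholly on assumed early-stop rates of 10-20% and SVR among stoppers of 10-20%. Durable SVR would be understated by 1 to 4 percentage points.

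Two stronger readings are not supported. The primary endpoint is not affected, because 24 weeks of follow-up reaches the SVR visit. Nor can one say that the race comparison is biased: with equal rates the 14-point design difference is unchanged, and with unequal rates the direction depends on figures the protocol does not give.

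**What to change.** Reconcile Sections 3.1, 3.5 and 4.5. State that any participant with undetectable HCV RNA at post-treatment week 24, whatever the duration of treatment, keeps the existing outcome visits at post-treatment weeks 36 and 48.

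In Section 6.0, state that in the durable-SVR analysis a participant with SVR is not scored as a failure solely because no week-48 sample was scheduled.

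The cost is a short amendment and one or two visits of an existing type for about 2-8 participants per group on the assumptions above, at most 8 × 2 = 16 visits per group. The analysis wording costs nothing. Only outcome collection changes; no dose or treatment rule is touched. The visit change has to be made while follow-up is running, because no later analysis can recover a sample that was never taken.

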4.0 Study Visits

4.1 Screening Visit 1: The first screening visit will take place no more than eight weeks prior to anticipated dose initiation. Written informed consent will be obtained prior to any screening evaluations. This initial screening visit will be used to determine patient eligibility as per the inclusion and exclusion criteria.

Screening visit 1						
Informed Consent	Main study (See Appendix 4)					
Race Determination	Self-administered questionnaire					
Medical History and						
Complete Physical	Include waist and hip circumference measurement					
Chest X-ray	Patients with pre-existing pulmonary disease					
EKG	Patients \geq 40 years of age					
CBC/Differential						
Chemistry	ALT, AST, AlkPO4, total and direct bilirubin, albumin, cholesterol, uric acid, BUN,					
	creatinine, glucose (non-fasting), alpha-fetoprotein					
Coagulation Tests	PT/PTT					
Thyroid Test	TSH					
Pregnancy Test	Urine					
Urinalysis	Routine chemistry and microscopic exam					
Viral Genetics	HCV genotype					
Viral Kinetics	HCV RNA quantitative					
Other Viral Serology	Anti HIV, anti-HCV					
	Documented within 12 months: HBsAg, HBcAb					
Other Serology and	Fe, TIBC, ferritin, iron saturation, ceruloplasmin (if clinically indicated), alpha-1-					
Chemistry (if not	antitrypsin, anti-nuclear antibody					
previously verified as						
normal)						
Liver Biopsy	Adequate tissue must be available within 18 months of screening visit					
Serum Storage	Serum 3 ml					
Education Video	"General Hepatitis C"					

Table 4 Screening Visit 1

Diabetics will be required to have a fundoscopic examination within one year before the end of screening.

4.2 Screening Visit 2: A second visit, to occur anytime in the 8-week period after the initial screening, is required prior to dosing initiation to perform baseline studies (blood drawing, measurement instruments) that will be used in analyses of therapeutic response.

Screening Visit 2						
Informed Consent	Genetics consent (See Appendix 4)					
Immunology (CD4/CD8)						
Questionnaires	Quality of Life, CES-D, Social Support Questionnaire, Self-efficacy					
	Questionnaire, Sexual Function Questionnaire					
Education Video	"Virahep-C Participation"					
Other	Aberrant laboratory studies requiring confirmation					

Table 5

4.3 Baseline Visit (Day 0): Once the patient has completed the two screening visits and has been confirmed to be eligible, he/she will return for additional laboratory studies and comprehensive instruction in self-injection techniques by study personnel. These three visits, screening 1, screening 2, and baseline (day 0) will occur within 56 days.

Interim Medical History	
CBC/Differential	
Chemistry	ALT, AST, AlkPO4, total and direct bilirubin, fasting triglycerides, glucose, insulin
Serum Storage	Serum 3ml
Viral Genetics	
Patient Genetics	
Viral Kinetics	HCV RNA quantitative
Pharmacokinetics	Peginterferon alfa-2a levels, 2',5'-OAS serum activity
Interferon Signaling	
Pregnancy Test	Urine
Adherence MATI	
Medication Education	Self-injection techniques (including video), use of MEMS caps, adherence materials
Study Medication Administration	Supervised by research coordinator

Table 6 Baseline (Day 0) visit

4.4 Treatment Period: Pegylated interferon will be administered as a weekly subcutaneous injection and ribavirin will be administered as tablets twice daily. Treatment will be continued for 48 weeks (except in the absence of virological response as defined below). During the treatment period, participants will return for safety and efficacy evaluations at weeks 1, 2, 4, 6 (safety labs only), and 8, and then monthly until treatment is completed.

Efficacy assessment at week 24 will determine if participants are eligible to continue the full 48 weeks of treatment. Participants who have a positive qualitative test result, in duplicate, will be discontinued from study medication at week 24. These participants will then enter the follow-up period and be followed for an additional 24 weeks (post-treatment weeks 4, 12, 24). If they begin other antiviral therapy, they will be discontinued from follow-up.

Interim Medical History	
Symptom-directed Physical Exam	Vital signs and weight at each visit; physical exam every 3 months or as needed
Adverse Event Assessment	
Concurrent Medication Assessment	
CBC/Differential	Each visit (except days 1 and 2)
Chemistry	Each visit except week 1; ALT, AST, AlkPO4, total and direct bilirubin, albumin, uric acid, BUN, creatinine, glucose. Fasting triglycerides, glucose, and insulin at week 24, and week 48 for responders only.
Pregnancy Test	Urine, each visit (except days 1and 2)
TSH	Weeks 12, 24, 36, 48
PT/PTT	Weeks 24 and 48
Viral Genetics	Days 1, 2, 7, 14, 28, and weeks 8, 12, and 24. For responders, at end of treatment (48 weeks)
Viral Kinetics	Days 1, 2, 7, 14, 28, and weeks 8, 12, 24, and 36. For responders, at end of treatment (48 weeks)
Pharmacokinetics (PEG-IFN alfa-2a levels 2',5'- OAS serum activity)	Days 1, 2, 7, 14, 28, and weeks 8, 12, and 24. For responders, at end of treatment (48 weeks)
Serum Storage	Each visit (except weeks 6, 16, 20, 28, 32, 40, 44)
Interferon Signaling	Days 1, 2, 7, 14, 28

Table 7Safety and Efficacy Visits

Immunology (CD4/CD8)	Weeks 8, 24, and end of treatment (week 48 for responders), or at early termination visit
CES_D*	Weeks 4, 12, 24, 48
Symptom Assessment	Each visit (except days 1 and 2)
Questionnaire*	
Brief MATI	Weeks 4, 12, 20, 28, 36
Gratitude Letter	Weeks 12, 36
Telephone Call	Week 24-26 (pending viral studies)
MEMS Use Questionnaire*	Weeks 4, 8, 12, 16, 20, 24, 28, 32, 36, 40, 44, 48
Adherence Questionnaire*	Weeks 4, 12, 24, 36, 48
Social Support and Self-	Week 24
efficacy Questionnaire*	
Sexual Function	Weeks 4, 12, 24, 48
Questionnaire*	
Adherence Videos	Weeks 1, 4, 12, 24, 36
Data Collection from Electronic	Weeks 4, 8, 12, 16, 20, 24, 28, 32, 36, 40, 44, 48
Monitors	

*Also assessed at the time of early termination for patients who discontinue prior to Week 24.

4.5 Follow-up Period: Participants will be followed for an additional 48 weeks following end of treatment. Participants who responded to therapy at week 24 will be treated for 48 weeks. They will return for post-treatment follow-up visits at follow-up weeks 4, 12, 24, 36, and 48. Non-responders will be followed for 24 weeks only. During these visits, participants will be evaluated for resolution of adverse events and laboratory studies will be drawn to measure efficacy. Participants will be contacted by telephone on one occasion between follow-up visits in order to foster continuity and encourage adherence with study follow-up.

Follow-up visit Procedures						
Interim Medical History						
Symptom-directed Physical	Vital signs and weight at each visit; physical exam at weeks 12, 24,					
Exam	and 48, and as needed					
Adverse Event Assessment						
Concurrent Medication						
Assessment						
CBC/Differential	Each visit					
Chemistry	Each visit: ALT, AST, AlkPO4, direct bilirubin					
	Follow-up weeks 12, 24, 48: albumin, uric acid, BUN, creatinine,					
	glucose					
	Follow-up week 24: fasting triglycerides, glucose, insulin					
Pregnancy Test	Urine, every visit					
TSH	Follow-up weeks 12, 24, 48					
PT/PTT	Follow-up weeks 12, 24, 48					
Serum Storage	Each visit					
Interferon Signaling	Any follow-up timepoint; at least n=72					
Viral Genetics	Each visit					
Viral Kinetics	Each visit					
Pharmacokinetics	Follow-up week12 for responders only					
(PEG-IFN alfa-2a only)						
Immunology (CD4)	Follow-up week 24					
Immunology (CD8)	Follow-up week 24; n=100					
CES_D	Follow-up week 24					
Symptom Assessment	Each visit					
Questionnaire						
Quality of Life	Follow-up week 24					
Sexual Function Questionnaire	Follow-up week 24					

Table 8 Follow-up Visit Procedures

4.6 Unscheduled Visits: Participants who have changes in severity or initiation of new symptoms, or who need to have laboratory tests repeated, will be asked to return to the study site for unscheduled evaluations. All additional evaluations will be included in the study record.

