Data Collection Procedures

At the beginning of the study, the study coordinator at each of the participating sites will be shipped a supply of the electronic compliance monitoring caps. Study coordinators will be trained to provide standardized instruction on electronic monitoring system use and participants will be given printed materials that explain the system.

At day 0, the pharmacy will dispense 180 ribavirin capsules in the original bottles supplied by the pharmaceutical manufacturer. In addition, the pharmacy will also dispense five pre-filled peginterferon syringes placed inside of opaque prescription bottles that accommodate MEMS caps. Lastly, pharmacies will provide needles for injection that fit the prefilled peginterferon syringes. Lids from both the ribavirin and peginterferon bottles will be replaced by the study coordinator with child-resistant MEMS caps. The opening and closing of the MEMS caps by the participant will electronically record dosing dates and times. Monitoring caps will be color coded to avoid inadvertently switching the two caps.

Electronic monitoring system follow-up will occur during the regularly scheduled monthly study visits. The follow-up will ensure that the monitors are placed on the refilled bottles of both medications and the MEMS caps are being used properly. During the visits, participants will complete a short four-item questionnaire that asks how the electronic monitors are being used. In addition, data collected from the monitors will be downloaded at each visit by the coordinator and sent electronically through a modem connection to a central database.

At completion of the study (i.e., weeks 24 or 48), the electronic monitoring system caps will be collected. Study sites will provide participants with \$25 for returning both caps undamaged.

Adherence Questionnaire. A detailed assessment of adherence is needed to understand whether variation in clinical outcomes is related to varying levels of adherence. This assessment is particularly important in individuals who fail maintenance therapy because failure may be related to behavioral variation subsequent to a change in therapy, characteristics of the new therapy, or low treatment efficacy. To distinguish between these potential factors, multiple measures of adherence and patient attitudes will also be assessed.

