A self-reported adherence questionnaire will be administered at weeks 4, 12, 24, 36, and 48. The questionnaire will ask participants about any doses missed during each of the previous four days and how medications are being taken. In addition, nine "yes/no" questions regarding compliance with the medication schedule will be asked as well as reasons for missing doses.

Other measurement tools: Social support questionnaire, self-efficacy questionnaire (see Appendix 6) will also be administered at Screen 2 visit, and at Week 24, or at early termination visit for patients who discontinue prior to Week 24.

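### The week-24 limit in the Table 7 footnote leaves participants who stop in weeks 25-47 without a termination CES-D, sexual function, adherence or MEMS-use questionnaire (minor)

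*Protocol*

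**What the plan says.** **Termination questionnaires.** The starred rows of Table 7 (Section 4.4) carry the note "Also assessed at the time of early termination for patients who discontinue prior to Week 24". The starred instruments are CES-D, symptom assessment, MEMS use, adherence, social support with self-efficacy, and sexual function.

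**Schedules of those instruments.** CES-D and sexual function are set at "Weeks 4, 12, 24, 48". For adherence, Section 5.4 states: "A self-reported adherence questionnaire will be administered at weeks 4, 12, 24, 36, and 48". MEMS use is every 4 weeks from week 4 to week 48. Symptom assessment is at every visit except days 1 and 2, and after week 8 visits are monthly to the end of treatment. Social support and self-efficacy have one on-treatment time. Section 5.4 places it at screening visit 2 "and at Week 24, or at early termination visit for patients who discontinue prior to Week 24".

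**Premature stops in general.** Section 3.5 sets no week limit but names blood only: "For those discontinued prematurely, blood samples will be obtained as listed for the week 48 end-of-treatment visit". It also encourages 24 weeks of follow-up. The immunology row of Table 7 allows for an early-termination visit, again without a week limit.

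**Follow-up.** Table 8 gives CES-D and sexual function at follow-up week 24 and symptom assessment at each visit. It has no row for the adherence or MEMS-use questionnaire.

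**Electronic caps.** Table 7 lists downloads every 4 weeks to week 48, in a row without a star. Section 5.4 also calls for a download at each visit. On return of the caps it says: "At completion of the study (i.e., weeks 24 or 48), the electronic monitoring system caps will be collected".

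**The concern.** The week-24 limit matches one starred row, social support and self-efficacy. For that row nothing is lost after week 24, because nothing more was planned on treatment. For CES-D, sexual function, adherence and MEMS use, a participant who completes treatment gives a week-48 form. One who stops in weeks 25-47 gives no form at the end of treatment, although the protocol foresees a termination contact and draws blood for it.

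The people affected matter for the secondary aims. Participants who are HCV RNA positive in duplicate stop at week 24 (Sections 3.1 and 4.4). Those still treated in weeks 25-47 are therefore week-24 responders, or have indeterminate or discordant results, and SVR is still possible for them. Aim 2 lists adherence among the on-treatment variables, Section 5.0 asks whether adherence explains a racial difference in SVR, and Section 6.0 puts adherence measures into the response models.

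The adherence questionnaire asks about doses missed over the previous four days and about reasons for missing doses. A form from week 24 therefore says little about the run-up to a stop at week 35, and the missing form cannot be reconstructed later.

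**Working it through.** The protocol states no figure on this point, so there is none to reproduce. The check compares schedules and counts weeks.

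**Inputs.** Schedules from Table 7 and Section 5.4; follow-up schedule from Table 8; termination rules from the Table 7 footnote and Section 3.5. Visits are assumed to fall on schedule, and follow-up weeks are counted from the stop.

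**Step 1: age of the last form at the stop.** For each stop week t = 25, ..., 47 (23 values), age = t minus the latest scheduled week not after t.

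- *CES-D and sexual function.* The last form is at week 24. Ages run 1, 2, ..., 23; the sum is 23 × 24 / 2 = 276; the mean is 276 / 23 = 12.0.
- *Adherence questionnaire.* The last form is at week 24 for t = 25-35 (ages 1 to 11, sum 66) and at week 36 for t = 36-47 (ages 0 to 11, sum 66). The mean is 132 / 23 = 5.7.
- *MEMS-use questionnaire.* Forms fall at weeks 24, 28, 32, 36, 40 and 44. Weeks 25-27 give ages 1, 2, 3 (sum 6); each of the five later 4-week blocks gives 0, 1, 2, 3 (sum 6). The mean is 36 / 23 = 1.6, maximum 3.
- *Symptom questionnaire and MEMS download.* Both have the same 4-weekly times in this window: mean 1.6, maximum 3.

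| Item | Scheduled in weeks 25-47 | Age at stop, weeks | Given after the stop |
|---|---|---|---|
| CES-D, sexual function | none | 1-23, mean 12.0 | follow-up week 24 |
| Adherence questionnaire | 36 | 0-11, mean 5.7 | never |
| MEMS-use questionnaire | 28, 32, 36, 40, 44 | 0-3, mean 1.6 | never |
| Symptom questionnaire | 28, 32, 36, 40, 44 | 0-3, mean 1.6 | each follow-up visit |
| MEMS download | 28, 32, 36, 40, 44 | 0-3, mean 1.6 | no row in Table 8 |

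**Step 2: distance between consecutive CES-D forms.** After a stop at week t the next form is at study week t + 24. The distance from the week-24 form is (t + 24) − 24 = t weeks, so 25 to 47 weeks. The longest case is a stop at week 47: next form at study week 71, and 71 − 24 = 47. A participant who completes treatment has 24 weeks between the week-24 and week-48 forms.

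**Step 3: does other text close the gap?** Section 3.5 covers any premature stop but prescribes blood only. Section 5.4 repeats the week-24 limit, and only for social support and self-efficacy, where it fits. Nothing else prescribes a termination form of the other four instruments after week 24.

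**Step 4: cap collection.** The only stated times are weeks 24 or 48. This gap does not come from the footnote, and it applies to stops before week 24 as well.

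**The case against.** The best case on the other side is that little is lost. The adherence-as-outcome analysis in Section 6.0 uses weekly dose intake from the MEMS caps, and the summary adherence statistics also come from them; self-report is a supplement. CES-D is not an endpoint in Section 2.2 and is not named in Section 6.0. The three mood questions in Section 3.4.4 are asked 4-weekly to week 48 and again in follow-up, and adverse events are asked about at each visit. The long CES-D gaps are worst cases, and completers also wait 24 weeks between forms. All of this stands, and it is why the point is minor. It does not explain why a week-24 limit is applied to forms that run to week 48.

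A reader might infer more than the documents support:

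- *That these participants leave with no symptom assessment.* The symptom form is starred, but it is also given at every monthly treatment visit and every follow-up visit.
- *That no MEMS download is scheduled for them.* Downloads run at weeks 28 to 44 and, by Section 5.4, at each visit. The footnote does not govern that row. At most about 3 weeks of dosing follow the last scheduled download, and the cap can still be read if it is brought back.
- *That non-adherence or mood effects will be understated, and more so in one race.* The documents do not establish a direction of bias.
- *That a definite number is affected.* If 60% of 400 (240) passed week 24 and 10-20% of these stopped early, 24 to 48 would be affected. The protocol gives neither rate, so the conclusion does not use this count.

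**Conclusion.** The point holds as a minor one. A stated rule, rather than a detail left for later, withholds the termination CES-D, sexual function, adherence and MEMS-use questionnaires from participants who stop in weeks 25-47. The practical loss is largest for CES-D and sexual function, smaller for the adherence questionnaire and slight for MEMS use. The adherence and MEMS-use forms are also absent from follow-up, so for them the last scheduled treatment form is final. Lack of a cap-collection time for any early stop is a separate, small gap.

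The loss falls on the secondary adherence data under Aim 2 and on the mood data. The primary SVR comparison does not use these forms and is unaffected. The sizes assume visits on schedule, and the means weight each stop week from 25 to 47 equally. How many participants are affected cannot be derived from the protocol.

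**What to change.** 1. In Table 7, change the footnote so that the starred questionnaires are also given at early termination before week 48. Give the social support and self-efficacy row its own mark that keeps the week-24 limit; the matching sentence in Section 5.4 can then stay as it is.
2. In Section 5.4 (Data Collection Procedures), state that both MEMS caps are downloaded and collected at any early-termination visit, as well as at weeks 24 or 48.

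The cost is one footnote, one sentence, and one set of existing forms at a visit where blood is already drawn. No new instrument or visit is needed, and the primary analysis does not change. Some participants who stop may decline the forms, so the change reduces the gap but may not remove it.
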